10.1.3. Assessment of Causality

The investigator is obligated to assess the relationship between the study drug and the occurrence of each AE or SAE. The investigator will use clinical judgement to determine the relationship. Alternative causes, such as natural history of the underlying diseases, concomitant therapy, and other risk factors, and the temporal relationship of the AE or SAE to the study drug will be considered and investigated. The investigator will also consult the IB and/or Product Information, for marketed products, in the determination of his/her assessment.

There may be situations when an SAE has occurred, and the investigator has minimal information to include in the initial report to the sponsor. However, it is very important that the investigator always provides assessment of causality for every SAE before transmission of the SAE report/eCRF to the sponsor since the causality assessment is one of the criteria used when determining regulatory reporting requirements. The investigator may change his/her opinion of causality in light of follow-up information, amending the SAE report/eCRF accordingly.

The causality of each AE should be assessed and classified by the investigator as “related” or “not related.” An AE is considered related if there is at least “a reasonable possibility” that the AE may have been caused by the study drug (ie, there are facts, evidence, or arguments to suggest possible causation, *or a causal relationship between the AE and the drug cannot be ruled out*). A number of factors should be considered in making this assessment, including:

- Temporal relationship of the AE to the administration of study treatment/study procedure
- Whether an alternative etiology has been identified
- Mechanism of action of the study drug
- Biological plausibility

An AE should be considered “related” to study drug if any of the following are met, otherwise the event should be assessed as not related:

- There is clear evidence to suggest a causal relationship, and other possible contributing factors can be ruled out.
- There is evidence to suggest a causal relationship, and the influence of other factors is unlikely.

- There is some evidence to suggest a causal relationship (eg, the AE occurred within a reasonable time after administration of the study drug). However, the influence of other factors may have contributed to the AE (eg, the patient's clinical condition or other concomitant AEs).

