11.3.3. Adverse Events

Adverse Events will be coded using MedDRA Version 18.1 or higher and graded using NCI-CTCAE Version 4.03 or higher. A treatment-emergent adverse event (TEAE) is defined as an AE that had an onset date on or after first study treatment or was worsening in severity from baseline (pretreatment) up to 30 days following permanent study treatment discontinuation or initiation of new anticancer therapy, whichever occurs first. All TEAEs will be included in summary tables and in patient data listings.

The incidence of TEAEs will be reported as the number (percentage) of patients with TEAEs by system organ class (SOC) and preferred term (PT). A patient will be counted only once by the highest grade according to [NCI-CTCAE Version 4.03](#) or higher within an SOC and PT, even if the patient experienced more than one TEAE within a specific SOC and PT. The number (percentage) of patients with TEAEs will also be summarized by relationship to the study treatment. Treatment-related AEs include those events considered by the investigator to be related to study treatment or with missing assessment of the causal relationship. Serious AEs, deaths, TEAE of Grade ≥ 3 , related

TEAEs and TEAEs that led to study drug/treatment discontinuation, dose reduction or treatment delay will be summarized.

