1 INTRODUCTION

The purpose of this statistical analysis plan (SAP) is to describe the procedures and the statistical methods that will be used to analyze the efficacy and safety endpoints and report results for BGB-290-104 protocol Version 2.0, dated July 23rd 2018: A Phase 1b/2 study to assess the safety, tolerability and efficacy of pamiparib in combination with radiation therapy (RT) and/or temozolomide (TMZ) in patients with first-line or recurrent/refractory glioblastoma (GBM). The focus of this SAP is for the planned primary, secondary efficacy and safety analyses specified in the study protocol.

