6.5.3 Adverse Events

The AE verbatim descriptions (investigator terms from the eCRF) will be classified into standardized medical terminology using Medical Dictionary for Regulatory Activities (MedDRA). Adverse events will be coded to MedDRA (Version 22.0 or higher), lower level term closest to the verbatim term. The linked MedDRA preferred term (PT) and primary system organ class (SOC) are also captured in the database.

A treatment-emergent adverse event (TEAE) is defined as an AE that had an onset date on or after first dose of study treatment or was worsening in severity from baseline (pretreatment) up to 30 days following permanent study treatment discontinuation or initiation of new anti-cancer therapy, whichever occurs first. All AEs, treatment emergent or otherwise, will be presented in patient data listings. TEAEs will be summarized and presented for all cohorts and all arms.

An overview table, including the number and percentage of patients with any TEAEs, any treatment-related TEAEs, treatment-emergent serious adverse events (SAEs), TEAEs with grade 3 or above, treatment-related SAEs, TEAEs that led to death, and TEAEs that led to treatment discontinuation, dose reduction or dose interruption will be provided. Treatment-related AEs include those events considered by the investigator to be unlikely, possibly or probably or definitely related to study drug or with missing assessment of the causal relationship. The overview table will be completed for each study Arm.

The following TEAEs will also be tabulated in summary tables for all arms and cohorts:

- TEAE
- SAE
- TEAEs with grade 3 or above
- Treatment-related TEAEs
- Treatment-related SAEs
- TEAEs that led to death
- TEAEs leads to treatment discontinuation
- TEAEs leads to dose reduction or dose interruption of either Pamiparib or RT or TMZ

A patient will be counted only once by the highest severity grade according to CTCAE v.4.03 within an SOC and PT, even if the patient experienced more than 1 TEAE within a specific SOC and PT. TEAEs with grade 3 or above will also be summarized by PT in descending order.

In addition, the following listings will be provided:

- Listing of all AEs,
- Listing of all SAEs
- Treatment-related AEs
- Grade 3 or above AEs
- AEs leading to death
- AEs leading to treatment discontinuation

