8 CHANGES IN THE PROTOCOL PLANNED ANALYSIS

1. Sample size reduction: The overall sample size was reduced during the study since the expansion cohorts were considered too large for this non-randomized and non-registrational study.
2. All arm B expansion cohort related analysis and language are removed since it was decided not to enroll expansion cohort for arm B

3. Primary analysis will be performed on efficacy analysis set, not safety analysis set. No sensitivity analysis will be performed.

4. Exploratory objectives and endpoints in the protocol will not be explored in this SAP

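### SAP 6.5.3 defines treatment-related AEs on a graded causality scale that conflicts with the protocol's related/not related classification, and the departure is not declared

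*SAP*

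**What the plan says.** Protocol section 10.1.3 sets the scale. "The causality of each AE should be assessed and classified by the investigator as" one of two values, related or not related. Related is drawn broadly and includes the case where "a causal relationship between the AE and the drug cannot be ruled out". The section then lists three situations that make an event related; "otherwise the event should be assessed as not related".

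Protocol section 11.3.3 sets the analysis rule: "Treatment-related AEs include those events considered by the investigator to be related to study treatment or with missing assessment of the causal relationship".

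SAP section 6.5.3 gives a different rule. An event is treatment-related if it is "considered by the investigator to be unlikely, possibly or probably or definitely related to study drug or with missing assessment" of causality. The rule feeds the overview table, which includes "any treatment-related TEAEs, treatment-emergent serious adverse events (SAEs), TEAEs with grade 3 or above, treatment-related SAEs", as well as separate tables of treatment-related TEAEs and SAEs and a listing of treatment-related AEs.

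The SAP states in section 1 that it will "report results for BGB-290-104 protocol Version 2.0, dated July 23rd 2018", the version that contains both protocol sections above. SAP section 8 lists four changes from the protocol's planned analysis: the smaller sample size, the dropped Arm B expansion, the change of primary analysis set with no sensitivity analysis, and exploratory endpoints ("Exploratory objectives and endpoints in the protocol will not be explored in this SAP"). AE causality does not appear there.

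**The concern.** The SAP's rule names four causality ratings, and the protocol asks investigators for none of them. It also places *unlikely* on the related side without comment. A programmer following the SAP would either find that the named values are missing from the data, or would move every unlikely event into the related tables.

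Attribution carries weight in this study. It is nonrandomized, so no concurrent control helps to separate drug toxicity from the effects of glioblastoma or radiotherapy. Readers will turn to the treatment-related tables for that, and they need to know which definition lies behind them.

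The same sentence ties relatedness to the study drug, whereas protocol 11.3.3 ties it to study treatment. For Arms A and B this leaves open whether an event attributed only to RT belongs in the related tables.

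**Working it through.** No sample size, power or event figure is involved, so the check is a comparison of texts followed by the two data structures that could lie behind them. The case report form is not among the documents, so both have to be worked through.

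**Case 1: the two-level field that protocol 10.1.3 describes.**

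| Recorded causality | Protocol 11.3.3 | SAP 6.5.3 |
|---|---|---|
| Related | counted | value not named |
| Not related | not counted | value not named |
| Missing | counted | counted |

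The only recorded state on which the two rules meet is missing causality. The SAP gives no instruction for the value *related*, so the programmer has to bring in a rule that the SAP does not contain. Protocol 11.3.3 is the obvious one.

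**Case 2: a graded field (an assumption; nothing in the protocol describes one).** Let D, P, S, U and M be the numbers of events rated definitely, probably, possibly, unlikely and missing. Four graded levels also imply a further level for unrelated events, which neither rule counts.

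- SAP count = D + P + S + U + M.
- Assume definitely, probably and possibly all map to related under protocol 10.1.3, and let u of the U unlikely events also qualify there, with 0 ≤ u ≤ U. The protocol count is then D + P + S + u + M.
- Excess = (D + P + S + U + M) − (D + P + S + u + M) = U − u.

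The excess is therefore between 0 (every unlikely event qualifies, u = U) and U (none does, u = 0). The documents give no counts by causality category for this study, so U has no value and the range cannot be narrowed.

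This is a count of events. The SAP tables count patients, once per system organ class and preferred term at the highest grade. A patient who already has a related event adds nothing to the any-treatment-related row when an unlikely event is reclassified, so a share of events does not carry over as the same share of patients.

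**Which outputs use the rule.** In SAP 6.5.3 these are the two treatment-related rows of the overview table, the treatment-related TEAE and SAE tables, and the treatment-related listing. The tables of all TEAEs, all SAEs, Grade 3 or above, fatal events and discontinuations do not use it. The Phase 1b primary endpoint in SAP 4.1 is the incidence, nature and severity of all AEs. DLTs are identified on the AE form (SAP 6.5.2) under protocol 4.2.4, which has its own requirement of relation to pamiparib.

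**Study drug or study treatment.** Protocol 11.3.3 says study treatment, and protocol 7.1.5.1 asks for relatedness to one or more study treatments. SAP 6.1 includes RT among the study treatments. Protocol 10.1.3, however, itself speaks of the study drug, so the inconsistency begins inside the protocol and the SAP repeats one side of it.

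**The case against.** The strongest defence is that counting unlikely events is deliberate caution. Protocol 10.1.3 calls an event related when causality cannot be excluded, and an event rated unlikely has not necessarily been excluded. This stands in part: some unlikely events could properly be related under the protocol, and a reviewer should not insist that all of them go to the other side. But the SAP does not offer this reason, and 10.1.3 leaves the decision to the investigator event by event rather than to a blanket recode.

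The second defence is that a two-level field would do little harm. The mismatch would surface at programming, and the protocol rule would be used. That is likely, and it means that usable tables can still be produced. It does not make the SAP's own rule workable.

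Third, the study is descriptive and not meant for registration, there is no between-arm safety test, and all AEs are listed as well. This limits the consequence but does not remove the conflict.

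A reader might infer more than the documents support:

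- *That the related-AE rate will be wrong whichever field was used.* With a two-level field a programmer would probably fall back on the protocol rule. With a graded field the excess could be zero.
- *That only missing-causality events would be tabulated.* This follows from a strictly literal reading in Case 1, but it is not a likely outcome.
- *That the Phase 1b primary endpoint or the DLT results are compromised.* Neither uses this rule.
- *That the SAP means to exclude RT-related events.* Protocol 10.1.3 uses the same term, and the SAP labels these events treatment-related, so intent to exclude is not shown.

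**Conclusion.** The SAP states a rule for treatment-related AEs that conflicts with the protocol version it analyses, and it does not declare the change. That much rests on the text alone and needs no assumption.

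The consequence depends on a case report form that is not available. With the protocol's two-level field, the rule cannot be applied as written. With a graded field, related events are overstated by between none and all of those rated unlikely; no percentage can be given. The effect is confined to the treatment-related rows, tables and listing. The point should be corrected because the conflict is plain, several safety outputs depend on it and the repair is cheap.

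**What to change.** Replace the sentence in SAP 6.5.3 with the protocol 11.3.3 rule: treatment-related means related to study treatment, or causality missing. Name pamiparib, TMZ and RT as the study treatments covered, which also settles the study drug question for Arms A and B.

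If a graded scale was in fact collected, the SAP should instead:

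- state the scale and all its levels;
- give its mapping to related and not related, and justify it under protocol 10.1.3, including where *unlikely* goes;
- show the unlikely events separately so that readers can see how much they contribute;
- record the change in SAP section 8.

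The cost is one sentence in the first case. In the second it is a short paragraph, an entry in section 8 and the separate display of unlikely events. Neither needs new data.

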6.5.4 Laboratory Values

Clinical laboratory values will be evaluated for selected parameters described in table 2.

Table 2. Serum Chemistry and Hematology Laboratory Tests

Serum Chemistry	Hematology
Alkaline phosphatase (ALP)	Hemoglobin
Alanine aminotransferase (ALT)	Platelet counts
Aspartate aminotransferase (AST)	White blood cell (WBC) count
Albumin	Neutrophil (Absolute)
Total bilirubin	Lymphocyte (Absolute)
Blood Urea Nitrogen	
Creatinine	
Chloride	
Phosphate	
Glucose	
Lactate dehydrogenase	
Total Protein	
Potassium	
Sodium	

ALP = alkaline phosphatase, ALT = alanine aminotransferase, AST = aspartate aminotransferases, WBC = white blood cell

For all quantitative parameters listed in Table 2, the actual value and the change from baseline to each postbaseline visit and to the end of treatment will be summarized by visit using descriptive summary statistics (n, mean, standard deviation, median, minimum, maximum for continuous variables). Qualitative parameters listed in Table 2 will be summarized using frequencies (number and percentage of patients), and changes from baseline to each postbaseline visit and to end of treatment will be reported using shift tables. Percentages will be based on the number of patients with non-missing baseline and relevant postbaseline results.

Laboratory parameters will be categorized according to NCI CTCAE version 4.03 grades and shifts from baseline CTCAE grades to maximum and the last postbaseline grades will be assessed. Laboratory parameters will be summarized by worst postbaseline CTCAE grade as well. For the lab tests with both high and low abnormality, separate records of worst CTCAE grade (for high and low) will be generated.

Patient data listings of selected hematology and serum chemistry parameters, urinalysis and coagulation will be provided.

6.5.5 Vital Signs

Descriptive statistics for vital sign parameters (systolic and diastolic blood pressure, pulse rate, temperature, height and weight) and changes from baseline will be presented by visit. Vital signs will be listed by patients and visits.

6.5.6 Electrocardiograms (ECG)

Single 12-lead ECGs will be collected at screening and end of treatment. Additional ECGs will be performed if clinically indicated. The percentage of patients with abnormal and clinical significant ECGs at EOT will be presented.

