4.1.2. Dose Expansion Phase (Phase 2)

Once the safety, tolerability, PK, pharmacodynamic, and preliminary antitumor activity have been reviewed for the dose escalation cohorts of each of the arms, up to approximately 60 patients may be enrolled in expansion cohorts for each of the 3 arms at a dose level below or equal to the MTD or MAD for that arm. In Arm C, 2 expansion cohorts may be opened, one for unmethylated GBM and one for methylated GBM ([Section 4.3](#)).

Approximately 60 patients may be enrolled during the dose escalation phase, and in each of the 4 dose-expansion cohorts totalling 240 patients in the dose expansion phase, for an approximate total of 300 patients enrolled in the entire study.

Adverse events (AEs) during and after the treatment period with study drug(s) will be followed and documented as outlined in [Section 8.4](#) and [Section 10](#). AEs will be graded according to National Cancer Institute Common Toxicity Criteria for Adverse Events (NCI-CTCAE) v4.03.

To determine the PK properties of pamiparib, blood samples will be taken at various time points as outlined in [Section 8.5](#) and [Appendix 1](#). To determine pharmacodynamic effects of pamiparib, blood samples will be obtained coinciding with specific PK time points as outlined in [Section 8.5](#) and [Appendix 1](#).

Disease status will be assessed using Response Assessment in Neuro-Oncology (RANO) criteria ([Appendix 2](#)). Patients will undergo tumor assessments at screening and then every 8 weeks, or as clinically indicated.

In Arm B expansion phase of the study, maintenance treatment (pamiparib in combination with TMZ) will be mandatory for all patients. In Arm A expansion phase of the study, continuation of treatment (with pamiparib in combination with TMZ) will be at the discretion of the investigator after discussion with the Medical Monitor.

Following completion of RT, all patients in Arms A and B who continue on pamiparib in combination with TMZ should follow the schedule of assessments for maintenance treatment ([Appendix 1 Table 4](#)).

Patients in Arms A and B who have completed all study treatments per protocol and do not continue on pamiparib in combination with TMZ (maintenance) should have their EOT visit at the end of the Rest Phase, 28 days after RT was completed, unless they do not complete the full study treatment; in such a case, they should have the end-of-treatment (EOT) visit within 7 days of stopping all study treatment.

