6.3. Treatment

Day 1 of Cycle 1 is the first day of any study treatment administration (there is no Day 0 in this protocol).

Details on study treatment are provided in [Section 7.1](#).

Study procedures of each clinic visit are outlined in [Appendix 1](#).

On days with PK assessments, study drug should be administered in the clinic in accordance with the schedule for the PK samples. Assessments should be obtained before study drug administration unless stated otherwise in [Appendix 1](#) and should be performed in order of least invasive to most invasive assessment. All safety-related assessments must be reviewed and dose modifications, if necessary, be made by the investigator or subinvestigator before study drug administration.

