6.5.2. End of Treatment Visit

Patients in Arms A and B who have completed all study treatments per protocol and do not continue on pamiparib in combination with TMZ will have their EOT visit at the end of the Rest Phase, 28 days after RT was completed. Patients continuing on pamiparib in combination with TMZ (maintenance) should follow the schedule of assessments for maintenance treatment ([Appendix 1 Table 4](#)).

All other patients with any of the reasons for discontinuation of study treatment listed above will undergo an EOT visit within 7 days after stopping all study treatments.

A visit should be scheduled as soon as possible, but the EOT visit may occur later after discussion with the medical monitor for specific circumstances, such as prolonged hospitalization. The visit at which MRI showed PD may be used as the EOT visit provided that all required assessments were performed. MRI does not have to be repeated if it was performed within 14 days of the EOT visit or at a prior response evaluation that documented PD. ECG does not have to be repeated if it was performed within 14 days of the EOT visit.

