11.3.7. Electrocardiogram

Electrocardiogram assessments will be performed as outlined in [Appendix 1](#). The percentage of patients with abnormal and clinically significant ECG findings will be presented.

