Appendix Table 3: Schedule of Assessments for Arm C (Pamiparib and Temozolomide) (Continued)

Study Phase	Screening ^a	Treatment ^b								End of Treatment ^c	Safety Follow-up ^d	Long-Term Follow-up ^d
		Cycle 1				Cycle 2		Cycle ≥3				
		D1	D8	D15	D22	D1	D15	D1	D15			
Concomitant medication(s) ^p	X	X	X	X	X	X	X	X	X	X	X ^p	X (~q12w) ^p
Pharmacokinetics ^q		X		X								
Blood for biomarkers ^r	X	X		X				X		X		
Tumor tissue ^s	X											
Survival follow-up												X (~q12w)

7/-14 to -1, Day -7/-14 to Day -1 of screening; aPTT, activated partial thromboplastin time; CSF, cerebrospinal fluid; D, day; ECG, electrocardiogram; ECOG, Eastern Cooperative Oncology Group; INR, International Normalized Ratio; MRI, magnetic resonance imaging; q8w ±7d, every 8 weeks ± 7 days; ~q12w, approximately every 12 weeks

^a Screening must occur within 28 days of Day 1. Assessments obtained within 14 days of Day 1 (pregnancy and laboratory assessments: within 7 days) do not have to be repeated on Day 1. Some assessments have a narrower screening window as shown in the table. It is highly recommended that general screening assessments such as physical examination and laboratory assessments should be conducted first to rule out ineligibility based on those grounds before more involved and/or invasive procedures are carried out.

^b Cycle 1 encompasses the dose-limiting toxicity (DLT) assessment window, and assessments of Day 1 of Cycle 2 at the end of the DLT assessment window are required for a patient to be DLT-evaluable. Assessments shown for Cycle 3 apply to all subsequent cycles except for MRI that occurs every second cycle (every 8 weeks).

^c The end-of-treatment (EOT) visit will occur within 7 days after a patient discontinued study treatment for any of the reasons outlined in [Section 6.5.1](#). A visit should be scheduled as soon as possible, but the EOT visit may occur later after discussion with the medical monitor for specific circumstances, such as prolonged hospitalization. The visit at which MRI showed progressive disease (PD) may be used as the EOT visit provided that all required assessments were performed. MRI does not have to be repeated if it was performed within 14 days of the EOT visit or at a prior response evaluation that documented PD. ECG does not have to be repeated if it was performed within 14 days of the EOT visit.

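### SAP 6.5.6 misstates the ECG schedule and limits its only ECG output to end of treatment, a narrowing of Protocol 11.3.7 that is not declared in SAP Section 8

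*SAP*

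**What the plan says.** SAP 6.5.6 describes collection as follows: "Single 12-lead ECGs will be collected at screening and end of treatment". It allows further ECGs when clinically indicated, then gives its one output: "The percentage of patients with abnormal and clinical significant ECGs at EOT will be presented". No other ECG table or listing is specified in the SAP. SAP 6.5 says that ECG findings contribute to the safety assessment but defines no ECG display.

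The protocol differs on both points.

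- **Schedule.** Protocol 8.4.3 and 11.3.7 refer ECG timing to Appendix 1. Appendix Tables 1 and 2 (Arms A and B) schedule screening, RT Day 1, RT Day 36 and EOT. Appendix Table 3 (Arm C) schedules screening, Day 1 of Cycles 1 and 2, Day 1 of Cycle 3 onwards, and EOT; footnote b repeats the Cycle 3 assessments, MRI apart, in every later cycle. Appendix Table 4 (maintenance) schedules re-screening, Cycle 1 Day 1 and EOT. Protocol 4.2.3 also includes an ECG among the assessments required at the end of the DLT window.
- **Analysis.** Protocol 11.3.7 says: "The percentage of patients with abnormal and clinically significant ECG findings will be presented". It sets no visit limit.

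SAP Section 8 lists four changes from the protocol: sample size, removal of the Arm B expansion, the primary analysis set with no sensitivity analysis, and exploratory endpoints. None concerns ECGs.

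**The concern.** The collection sentence in SAP 6.5.6 does not describe the protocol's schedule, and the words at EOT narrow the planned analysis without a declaration. A programmer who follows the section would leave scheduled on-treatment ECGs out of the only ECG output. A reader of the study report would not learn that the protocol's analysis had been cut.

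ECG is treated differently from its neighbours. Laboratory values are summarised by visit and by worst post-baseline grade (SAP 6.5.4), vital signs by visit with a listing (6.5.5), and ECOG status by visit (6.5.7).

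EOT is also not one time point within an Arm A or B column. Under Protocol 4.1.2, patients who complete treatment and "do not continue on pamiparib in combination with TMZ (maintenance) should have their EOT visit at the end of the Rest Phase" are read 28 days after radiotherapy, whereas early stoppers are read within 7 days of stopping. For maintenance patients, footnotes a and j of Appendix Table 4 also use EOT for the post-rest visit, while the table has its own EOT column after maintenance. SAP 6.5.6 does not say which visit counts.

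**Working it through.** The plan gives no figure to reproduce. The check compares the schedules and counts what an EOT-only table leaves out, using nominal study days.

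**Inputs**

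- Arm C: ECG on Day 1 of each 28-day cycle (Appendix Table 3, footnote b), so Days 29, 57, 85 and so on after Cycle 1.
- The Cycle 1 Day 1 ECG is treated as baseline. Protocol 6.3 says "Assessments should be obtained before study drug administration unless stated otherwise in" the appendix, and a screening ECG within 14 days can replace it.
- Reuse rule, Protocol 6.5.2: "ECG does not have to be repeated if it was performed within 14 days of the EOT visit".
- Arms A and B completers without maintenance: EOT at Study Day 71 to 78 (Appendix Tables 1 and 2).
- DLT window, Protocol 4.2.3: combination period plus 4 weeks in Arms A and B; 28 days in Arm C.

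**Arm C**

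A patient who starts N cycles has N-1 scheduled on-treatment ECGs after baseline. Cycle Day 1 ECGs are 28 days apart, so at most one can stand in for the EOT ECG under the 14-day rule. Omitted: N-1 without reuse, N-2 with reuse.

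| Cycles started (assumed) | On-treatment ECGs | Omitted |
|---|---|---|
| 2 | 1 | 0 to 1 |
| 3 | 2 | 1 to 2 |
| 4 | 3 | 2 to 3 |
| 6 | 5 | 4 to 5 |

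The ECG at Cycle 2 Day 1, which closes the Arm C DLT window, is among those omitted unless it is reused.

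One case follows from the protocol's own MRI schedule. Protocol 6.5.2 says: "The visit at which MRI showed PD may be used as the EOT visit provided that all required assessments were performed". If progression is found at the k-th scheduled MRI and that visit serves as EOT, EOT is Day 56k + 1 and there are 2k - 1 earlier on-treatment ECGs:

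- k = 1: Day 57, 1 omitted
- k = 2: Day 113, 3 omitted
- k = 3: Day 169, 5 omitted

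The nearest earlier ECG is 28 days before EOT. With the MRI 7 days early and that ECG 3 days late, the gap is 28 - 7 - 3 = 18 days, still outside the 14-day rule.

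**Arms A and B, radiotherapy period**

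For completers without maintenance, RT Day 36 is 71 - 36 = 35 to 78 - 36 = 42 days before EOT. It cannot be reused and is omitted.

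In Phase 1b, the end-of-DLT-window ECG compares with EOT at Day 71 to 78 as follows:

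| Combination period | Window end | Gap to EOT | Within 14 days |
|---|---|---|---|
| Arm A, 2 weeks | 2 + 4 = 6 weeks, Day 42 | 29 to 36 days | No |
| Arm A, 4 weeks | 4 + 4 = 8 weeks, Day 56 | 15 to 22 days | No |
| Arm A, 6 weeks | 6 + 4 = 10 weeks, Day 70 | 1 to 8 days | Yes |
| Arm B, 3-week example in Protocol 4.2.3 | 3 + 4 = 7 weeks, Day 49 | 22 to 29 days | No |

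Only the 6-week schedule clearly coincides with EOT. The 4-week case misses by as little as one day, so visit timing could change it for some patients.

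**Maintenance**

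Appendix Table 4 schedules no ECG between Cycle 1 Day 1 (pre-dose) and EOT. No scheduled ECG taken during maintenance dosing is lost, provided EOT is read as the visit after maintenance.

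**The case against.** The strongest reply is that little safety information is lost. Protocol 10.1.5 requires ECG abnormalities judged clinically significant to be recorded as AEs or SAEs at whatever visit they occur, and SAP 6.5.3 tabulates treatment-emergent AEs and lists all AEs. If the ECG output means abnormalities that are also clinically significant, the same findings should already be in the report, and what is missing is mainly a separate ECG display. ECG is not named in any primary or secondary endpoint. All of this stands, and it sets the grade at minor. It does not correct the schedule sentence or declare the narrowing.

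Several stronger readings are tempting, and the documents do not support them.

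- **One percentage pooled across arms.** SAP 6.5 presents safety by dose cohort and arm, with Phase 1b and Phase 2 in separate columns. The mixing of EOT timings is within an Arm A or B column.
- **Most Arm C ECGs are certainly lost.** With reuse, the omission is 0 of 1 at two cycles and 1 of 2 at three. Cycles per patient are not given.
- **Thirty Arm C patients are affected.** Thirty is the expansion enrolment in SAP Section 5, not the number who reach Cycle 2.
- **Arms A and B lose only the Day 36 ECG.** This understates Phase 1b, where the end-of-DLT-window ECG can also fall outside EOT.
- **Off-drug EOT readings hide a drug effect.** The documents do not link pamiparib concentration to ECG change, and Protocol 1.3.4.1 reports no QT prolongation in dogs.
- **The scheduled ECGs will not be taken.** The SAP analyses protocol Version 2.0, whose Appendix 1 still requires them; the defect is in the analysis text.

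**Conclusion.** The point holds as a minor safety-reporting error. SAP 6.5.6 contradicts Appendix 1 on when ECGs are taken, narrows Protocol 11.3.7 to EOT, and Section 8 does not say so.

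The size in Arm C is N-2 to N-1 of N-1 scheduled on-treatment ECGs per patient, the lower figure only when the last is reused as the EOT ECG. In Arms A and B it is the Day 36 ECG for completers, plus, in Phase 1b, the end-of-DLT-window ECG where it does not coincide with EOT. The counts assume nominal visit days and that Cycle 1 Day 1 is pre-dose; the number of cycles is an assumption shown over a range. The minor grade assumes that investigators record clinically significant ECG findings as AEs, as Protocol 10.1.5 requires. Efficacy is unaffected.

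**What to change.** In SAP 6.5.6:

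1. Replace the collection sentence with the Appendix 1 schedule for each arm and for maintenance, and add the end-of-DLT-window ECG from Protocol 4.2.3.
2. Present the percentage of patients with abnormal and clinically significant ECG findings at any post-baseline visit, as Protocol 11.3.7 plans. Show EOT separately if wanted.
3. State which EOT visit applies to patients who go on to maintenance.

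If the EOT limit is kept, declare it in Section 8 as a change from Protocol 11.3.7. Splitting abnormal findings by clinical significance is optional; it would show abnormalities that do not reach the AE tables.

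The cost is a few sentences and about one extra table, from ECGs the protocol already requires.
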